4 RESEARCH QUESTION/AIM(S)

Can machine learning, using a broad range of variables including parent reported risk factors, be used to predict the risk of neonatal early-onset sepsis with greater accuracy than current local guidelines in low-resource settings (LRS)?

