STUDY FLOW CHART	7
1. BACKGROUND	9
2. RATIONALE	10
3. THEORETICAL FRAMEWORK	10
4. RESEARCH QUESTION/AIM(S)	15
5. STUDY DESIGN/METHODS	16
6. STUDY SETTING	19
7. SAMPLE AND RECRUITMENT	20
8. ETHICAL AND REGULATORY COMPLIANCE	25
9. DISSEMINATION POLICY	28
10. REFERENCES	29
11. APPENDICES	34

ABBREVIATIONS

CI	Chief Investigator
CRF	Case Report Form
ICF	Informed Consent Form
ISF	Investigator Site File
NHS	National Health Service
NIHR	National Institute for Health Research
PI	Principal Investigator
REC	Research Ethics Committee
SGUL	St Georges, University of London
JRES	(St Georges) Joint Research and Enterprise Services
WHO	World Health Organisation
ROM	Rupture of membranes
EOS	Early onset sepsis
LOS	Late onset sepsis
PCR	Polymerase chain reaction
LRS	Low resource setting

KEY STUDY CONTACTS

Chief Investigator	
Principal Investigator (In-Country)	
Study Co-ordinator	
Sponsor	St George's, University of London
Funder(s)	CREATE (Africa Health Research Training Programme) Wellcome Trust
Key Protocol Contributors	

STUDY SUMMARY	
Study Title	Using machine learning to model early-onset neonatal sepsis risk in Uganda
Internal ref. no. (or short title)	NeoRisk
Study Design	Observational
Study Participants	Neonates born at ≥ 34 weeks' gestational age at Kawempe Hospital in Kampala, Uganda (Phase 1) or Sally Mugabe Central Hospital in Harare, Zimbabwe (Phase 3)
Planned Size of Sample (if applicable)	1600 (Phases 1+2), 900 (Phase 3)
Follow up duration (if applicable)	1 month post-delivery
Planned Study Period	September 2023-May 2024
Research Question/Aim(s)	
1. Determine antenatal and perinatal factors associated with early-onset neonatal sepsis in low-resource settings, as diagnosed by a blood culture or a senior clinician2. Measure the strength of association between the above factors and early-onset neonatal sepsis3. Combine the above risk factors into a risk stratification model for early-onset neonatal sepsis using machine learning techniques
FUNDING AND SUPPORT	
FUNDER(S)	FINANCIAL AND NON FINANCIAL SUPPORT GIVEN
CREATE PhD Programme	

ROLES AND RESPONSIBILITIES OF STUDY MANAGEMENT COMMITTEES/GROUPS & INDIVIDUALS

The study has been discussed with the Community Engagement team at Makerere University-Johns Hopkins University Research Collaboration in Kampala, Uganda, which works with clinical studies at Kawempe Hospital.

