4.1 Objectives

[figure not shown]
1. Determine risk factors for neonatal early-onset sepsis in Kampala, Uganda
2. Use machine learning techniques to create a risk stratification model for early-onset sepsis in Uganda
3. Explore relationship between culture-positive sepsis and clinical diagnostic features in Uganda using machine learning techniques, including association between level of training of clinician documented diagnosis and blood culture result
4. Validate the model from Uganda externally using an independent dataset from a neonatal population in Harare, Zimbabwe

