4.2 Outcome

- Primary outcome for Phase 1: Positive blood culture amongst neonatal participants
- Primary outcome for Phase 3: Clinician (specialist neonatal or paediatric doctor) diagnosis of sepsis amongst neonatal participants as documented in clinical notes or discharge letter
- Clinical features of neonatal sepsis as listed in GAIA neonatal infections case definition
- Admission to neonatal unit
- Readmission to hospital in first 28 days amongst neonatal participants
- Death before 28 days of age
- Sensitivity, specificity, positive and negative predictive value of risk stratification model for participants in Kampala and Harare

Using machine learning to model early-onset neonatal sepsis risk in Uganda (NeoRisk)

5 STUDY DESIGN and METHODS of DATA COLLECTION AND DATA ANALYSIS

There will be three main phases to this study, which is an observational cohort study.

Using machine learning to model early-onset neonatal sepsis risk in Uganda (NeoRisk)

Phase 1 will take place at Kawempe Hospital in Kampala, Uganda. Participants will be recruited from labour wards by study staff, and interim analysis will be completed after recruitment of 10% of the total sample. See section 7.3 for further details.

Data will be collected via an online CRF, including the factors listed in the table in Section 3.

Additionally:

- All neonates within the study will have a **neonatal venous blood sample** taken for culture by designated study staff
 - This must be taken before administration of antibiotics or within 48 hours of birth, whichever is sooner, and regardless of whether the neonate is being investigated and treated for sepsis.
- **Postnatal information** will be collected via telephone at 1 month including maternal and infant outcome, hospital readmission or clinical illness, and vaccines given

All data will be checked for quality control by a member of the study team.

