The focus groups will be conducted by members of MUJHU's social sciences team and [name]. A tool has been developed by the social sciences team and [name] for these discussions (see attached). The discussions will be recorded, and recordings destroyed once the discussions have been transcribed. The social sciences team will then complete thematic analysis of the discussions.

We anticipate Phase 1 will take place between January and July 2024.

Phase 2 will use the data collected in phase 1 to construct a risk stratification model, in collaboration with the Advanced Research Computing Centre at University College London.

We anticipate Phase 2 will take place between March and September 2024.

Using machine learning to model early-onset neonatal sepsis risk in Uganda (NeoRisk)

Phase 3 will involve external validation of the risk stratification tool. This phase will take place at Sally Mugabe Central Hospital in Harare, Zimbabwe. Participants will be recruited from antenatal clinics and labour wards by study staff.

The same data will be collected from participants in Phase 3 as in Phase 1. Ideally, data collection will take place via the Neotree platform(41) – this will be decided once the factors included in the model have been determined, and whether they are already in routine collection via Neotree. If the Neotree platform will not capture sufficient data to match the inputs of the model, an online CRF will be created as in Phase 1 via REDCap. This decision will be made in collaboration with the local study team prior to the start of recruitment.

The primary outcome for Phase 3 will be senior clinician diagnosis of sepsis recorded within 48 hours of delivery, and blood cultures (when available) will only be taken in neonates judged to be at risk of, or with clinical signs of sepsis as per standard clinical guidelines. Using senior clinician diagnosis of sepsis as the outcome is because supply of blood culture bottles and laboratory analysis of cultures is unreliable and is unlikely to be available to all study participants as in the Phase 1 setting. The risk stratification model will be applied to these data to determine its accuracy in a second population and explore its generalisability.

We anticipate Phase 3 will take place between September 2024 and March 2025.

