The TRIPOD (Transparent reporting of a multivariable prediction model for individual prognosis or diagnosis) statement have been followed in the design of this study and will be followed in its reporting(42). Adjustments will be made as necessary with the release of upcoming artificial intelligence-specific guidelines.

Data analysis

Phase 2 will constitute the main data analysis for data from Uganda.

There will be two main streams to data analysis, which will be completed using R and in collaboration with the Advanced Research Computing Centre at UCL.

1. Machine learning analysis:
 - a. Data from Phase 1 will form a ‘training data set’, with 20% reserved for testing and validation, and be fed into a pre-programmed machine
 - b. Previous methods used for sepsis prediction that will be investigated include gradient tree boosting and neural networks
 - c. Bootstrapping will be considered
 - d. Determination of the exact machine learning model will depend on the data obtained, but the following will be considered:
 - i. Weighted inputs: Allows scaling of measurements
 - ii. Conformal prediction: Allows the machine to determine how uncertain its prediction is, based on distribution of data it has, and missing data
 - iii. Recurrent neural networks: Allows the machine to recognise time-dependent patterns
 - iv. Gradient descent: A method of ‘training’ a machine to minimise the error between prediction and reality by gradually adjusting its weights
2. Traditional logistic regression will be used to identify risk factors associated with clinical and microbiological diagnoses of neonatal sepsis. Although the principal model will be created using machine learning techniques, logistic regression will be

Using machine learning to model early-onset neonatal sepsis risk in Uganda (NeoRisk)

used as a second check of results and to provide additional context with which to interpret the machine learning model

For **Phase 3**, data will be inputted to the machine learning model from Phase 2, and the sensitivity, specificity, positive predictive and negative predictive values calculated, as well as the AUC value.

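### Section 4 asks whether the model is more accurate than current local guidelines, but the plan as written produces no guideline accuracy and no model-versus-guideline difference

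*Combined protocol and SAP*

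**What the plan says.** The research question in Section 4 is comparative. It asks whether machine learning can "be used to predict the risk of neonatal early-onset sepsis with greater accuracy than current local guidelines in low-resource settings".

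The parts of the plan that should carry this out have no comparator:

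- **Study Summary, aims.** Two aims concern risk factors and their strength of association. The third is to "Combine the above risk factors into a risk stratification model for early-onset neonatal sepsis using machine learning techniques".
- **Section 4.1, objectives.** These cover risk factors, building the model, the relation of culture to clinical features, and external validation. The closest to current practice is objective 3, "including association between level of training of clinician documented diagnosis and blood culture result".
- **Section 4.2, accuracy outcome.** "Sensitivity, specificity, positive and negative predictive value of risk stratification model for participants in Kampala and Harare".
- **Section 5, data analysis, Phase 2.** Machine learning is applied to the Phase 1 data "with 20% reserved for testing and validation". A second stream is described thus: "Traditional logistic regression will be used to identify risk factors associated with clinical and microbiological diagnoses of neonatal sepsis". It also serves as a check on the machine learning results.
- **Section 5, data analysis, Phase 3.** The data are run through the model and "the sensitivity, specificity, positive predictive and negative predictive values calculated, as well as the AUC value".
- **Section 7.2.1, sample size.** The diagnostic-test calculations size the sensitivity of one test, at 90% sensitivity with prevalence 5% (Phase 1) and 16% (Phase 3). The further Phase 1 methods are for a single prediction model.

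Clinical guidelines have one operational role in the study: in Phase 3, blood cultures will "only be taken in neonates judged to be at risk of, or with clinical signs of sepsis as per standard clinical guidelines".

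**The concern.** A question of the form 'is A more accurate than B' needs an estimate for A, an estimate for B, and their difference in the same infants. The plan provides only the first. A conclusion that the model improves on local guidelines would then have to borrow guideline accuracy from other populations or outcome definitions, or rest on a guideline definition and threshold chosen after the results were seen.

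Two provisions in Section 5 could also remove the inputs that a later comparison would need. After the pilot of 160 participants, the data collection instrument may be shortened by dropping factors that seem unrelated to outcome. In Phase 3, the choice of data platform turns on whether it captures the model's inputs; the guideline's inputs are not considered.

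**Working it through.** **1. What the plan's own figure sizes.** Section 7.2.1 gives 1460 for Phase 1 (sensitivity Se = 0.90, prevalence 0.05, 95% confidence) without stating the half-width d. The single-test formula is N = 1.96² × Se(1 − Se) / (d² × prevalence). Solving for d:

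- Phase 1: 1460 × 0.05 = 73 cases; d = 1.96 × √(0.09/73) = 0.069.
- Phase 3: 900 × 0.16 = 144 cases; d = 1.96 × √(0.09/144) = 0.049.

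The figure of 1460 is therefore reproduced only by solving for an unstated d. Neither calculation contains a guideline accuracy, a discordance or a difference.

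**2. What each section would deliver if followed exactly.**

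| Source | Model accuracy | Guideline accuracy | Difference |
|---|---|---|---|
| Section 4, question | asked | asked | asked |
| Study Summary, aims | model built | no | no |
| Section 4.1, objectives | validation | no | no |
| Section 4.2, accuracy outcome | yes | no | no |
| Section 5, data analysis | yes | no | no |
| Section 7.2.1, sample size | one test | no | no |

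Objective 3 relates clinician diagnosis to culture. A clinician's diagnosis is not a guideline classification, and nothing sets it beside the model. The focus groups cover current diagnostic strategies qualitatively.

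**3. Precision if a paired comparison were added (illustrative).** From the documents: 1600 infants and 5% prevalence give 80 cases and 1520 non-cases. A 20% hold-out is 320 infants, with 320 × 0.05 = 16 cases. Assumed, because the documents give no figure: the proportion of infants classed differently by the two methods, taken as 10% to 30%, and no true difference.

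Half-width = 1.96 × √(discordant proportion / n)

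| n | 10% | 20% | 30% |
|---|---|---|---|
| 80 cases | 6.9 points | 9.8 | 12.0 |
| 16 cases | 15.5 | 21.9 | 26.8 |

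At 16 cases and 20% discordance there are only about 3 discordant pairs (16 × 0.20 = 3.2), so that row is a rough guide. For specificity, the same formula with 1520 non-cases gives 1.6 to 2.8 points. Sensitivity is the limiting quantity.

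**4. Power (illustrative).** Assumed: model sensitivity 90% and a two-sided 5% exact McNemar test. Ranges run over independent and fully nested errors.

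| Guideline sensitivity (assumed) | 80 cases | 16 cases |
|---|---|---|
| 70% | 85% to 99.9% | 8% to 11% |
| 80% | 34% to 82% | about 2% or less |
| 85% | 11% to 21% | under 1% |

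The analysis set matters as much as the decision to compare: all Phase 1 infants can detect a large difference, while the hold-out alone cannot.

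**The case against.** **The comparator is one phrase.** The Study Summary has its own list of aims with no comparator, and the objectives, outcome and analysis agree with that list. All four objectives can be met as planned. This stands: the comparison is not the study's only aim, and rewording Section 4 would also remove the mismatch. It does not remove the gap while Section 4 stands as written.

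**The data may allow the comparison later.** A reader might infer that the study is unable to answer its question. The documents do not support that. Every Phase 1 neonate is cultured whether or not sepsis is suspected, and established risk factors and clinical signs are collected. What is missing is the specified analysis.

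**The comparison may be harder than it looks.** A reader might equally infer that the guideline classification is already on the CRF. That cannot be confirmed: no guideline is named, the risk-factor table in Section 3 is incomplete in the copy available, and Section 1 warns that gestational age and duration of membrane rupture may be unknown.

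**Universal culture does not make the comparison unbiased.** It removes selective verification in Phase 1, and no more than that. Sampling is by convenience (Section 7.2.2). Signs are recorded over 72 hours while culture results go to clinicians in real time, so later signs may be recorded with the result known. Section 3 cites 6 to 16 culture-negative cases per culture-positive one. These limits stand and shape the fix.

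**Same-cohort context exists.** Clinician diagnosis is recorded in the same infants and will be related to culture. This is useful background on current practice, but it measures neither guideline accuracy nor a difference from the model.

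**Conclusion.** The point holds: Section 4 poses a model-versus-guideline question, and the plan as written gives no guideline accuracy and no difference. This rests on reading the sections together and on no assumed number.

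The precision figures are illustrations under an assumed discordance of 10% to 30% and no true difference: about 7 to 12 points with 80 cases and about 15 to 27 points with 16. The case counts also depend on the 5% prevalence in Section 7.2.1, which the protocol gives as an upper figure from unpublished data. Fewer cases would widen every interval.

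The documents do not support saying that the study cannot answer the question with its data, that an unbiased comparison is there for the taking, or that the guideline inputs are known to be recorded. The gap should be closed before the post-pilot revision of the CRF and before Phase 2 modelling.

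**What to change.** 1. Name the local guideline in use at each site. Define guideline-positive and guideline-negative from specific CRF fields, with a rule for missing inputs.
2. Confirm that those fields are collected, exempt them from the post-pilot shortening, and add them to the criteria for choosing the Phase 3 data platform.
3. Prespecify, as the analysis that answers Section 4, a paired comparison of model and guideline against Phase 1 culture. Report differences in sensitivity and specificity with 95% CIs.
4. Use out-of-sample predictions (cross-validated or bootstrap-corrected) in all Phase 1 infants. This goes beyond the planned 20% reserve, which may stay for its own purpose. If the model's threshold is matched to the guideline's specificity or sensitivity, the CI should reflect that the threshold is estimated.
5. Use only signs recorded before the culture result is known.
6. Treat Phase 3 as supportive. Clinician diagnosis there may itself be shaped by the guideline, and culture is taken selectively.
7. If the guideline classification cannot be derived, reword Section 4 to drop the comparative claim and align it with the Study Summary and Section 4.1.

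Cost: one derived variable and one extra analysis, with no new patients or procedures. The comparison will be limited by how completely the guideline inputs are recorded.

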4.1 Objectives

[figure not shown]
1. Determine risk factors for neonatal early-onset sepsis in Kampala, Uganda
2. Use machine learning techniques to create a risk stratification model for early-onset sepsis in Uganda
3. Explore relationship between culture-positive sepsis and clinical diagnostic features in Uganda using machine learning techniques, including association between level of training of clinician documented diagnosis and blood culture result
4. Validate the model from Uganda externally using an independent dataset from a neonatal population in Harare, Zimbabwe

4.2 Outcome

- Primary outcome for Phase 1: Positive blood culture amongst neonatal participants
- Primary outcome for Phase 3: Clinician (specialist neonatal or paediatric doctor) diagnosis of sepsis amongst neonatal participants as documented in clinical notes or discharge letter
- Clinical features of neonatal sepsis as listed in GAIA neonatal infections case definition
- Admission to neonatal unit
- Readmission to hospital in first 28 days amongst neonatal participants
- Death before 28 days of age
- Sensitivity, specificity, positive and negative predictive value of risk stratification model for participants in Kampala and Harare

Using machine learning to model early-onset neonatal sepsis risk in Uganda (NeoRisk)

5 STUDY DESIGN and METHODS of DATA COLLECTION AND DATA ANALYSIS

There will be three main phases to this study, which is an observational cohort study.

Using machine learning to model early-onset neonatal sepsis risk in Uganda (NeoRisk)

Phase 1 will take place at Kawempe Hospital in Kampala, Uganda. Participants will be recruited from labour wards by study staff, and interim analysis will be completed after recruitment of 10% of the total sample. See section 7.3 for further details.

Data will be collected via an online CRF, including the factors listed in the table in Section 3.

Additionally:

- All neonates within the study will have a **neonatal venous blood sample** taken for culture by designated study staff
 - This must be taken before administration of antibiotics or within 48 hours of birth, whichever is sooner, and regardless of whether the neonate is being investigated and treated for sepsis.
- **Postnatal information** will be collected via telephone at 1 month including maternal and infant outcome, hospital readmission or clinical illness, and vaccines given

All data will be checked for quality control by a member of the study team.

A blood culture will be taken from all neonatal participants at birth, prior to starting antibiotic treatment wherever safe to do so. The volume of blood taken for culture must be 1-2ml and will be verified by weighing blood culture bottles. Training will be provided to paediatric and study teams on blood culture sampling methods, including adequate cleaning of the skin prior to sampling. Feedback on sample volumes and contamination rates (see section 7.3 for definition) will be fed back to paediatric consultants, and additional staff training offered. Where sample is remaining after 3ml is added to the culture bottle, the excess will be retained as a blood spot sample for use in future ethically approved research, where the participant has consented to this.

The results of the microbiological tests will be communicated to the participant's clinical team in real time – see section 7.3.4 for further details. Clinician diagnosis of sepsis will be recorded where a clinician of registrar level or above has recorded a diagnosis of sepsis within 48 hours of birth. To reduce the subjectivity of this measure, GAIA level of certainty for a diagnosis of sepsis will also be assessed (35) and the level of diagnostic certainty recorded (1-5, as per GAIA criteria). Medical records are recorded on paper at Kawempe Hospital, before being coded into an electronic medical record by data clerks. PDF scans of medical records will be available where detailed review is required.

All participant data will be collected by trained study staff, and recorded into an online CRF hosted on REDCap, a secure web application. No patient identifiable data will be stored on the main REDCap database. See section 8.6 for further details of data management plans.

The postnatal information will be completed via a telephone call at 28 days post-delivery, made by study staff. Participants' contact number, a contact number for their partner, and a contact number for a second friend or family member will be taken at recruitment to minimise loss to follow up due to changes to mobile telephone number. Participant identity will be confirmed using three factors (date of birth, full name, address/village). The following information will be collected:

- Health status of mother and baby
- Any visits to medical care for the neonate
 - If attended or admitted to Kawempe hospitals, these electronic medical records will be reviewed by study staff

Using machine learning to model early-onset neonatal sepsis risk in Uganda (NeoRisk)

- If attended elsewhere, the mother will be asked the reason for presenting, whether the neonate was admitted to hospital, the main diagnosis, and any treatments given.

Recruitment of the first 160 participants from labour ward (10% of the overall sample) will be treated as a pilot, and both recruitment and data will be reviewed at this point with particular attention to the following aspects:

- Demographic comparison between recruited women and the population attending Kawempe
- Data completion
- Volume of blood culture samples taken
- Loss to follow up rates
- Association between potential risk factors and clinical sepsis, or culture-positive sepsis

After this pilot analysis, the data collection instrument may be adjusted to be more concise if some risk factors appear to have no relationship with neonatal outcomes. Additionally, the recruitment strategy may be adjusted to include women attending antenatal clinics to improve the representativeness of the sample if the pilot sample is significantly different demographically to the general population of pregnant women attending the same study site antenatally. Finally, feedback and staff training will be given as needed to ensure optimal sample volumes and data completeness.

During Phase 1, two separate focus group discussions with 10 participants each will be held with staff from Kawempe Hospital. One discussion will be with senior clinicians, and one with junior clinicians and midwives. The focus groups will be held on site at Kawempe in English. Focus groups are being held in order to complement the quantitative results of this project by highlighting risk factors currently perceived as significant (which should then be a key part of analysis and results dissemination to confirm their usefulness), inform of current diagnostic difficulties to guide future work with the risk stratification model, and provide context for development and communication of the model to maximise its utility. The focus groups will address the following issues:

- Ascertain knowledge and awareness of neonatal sepsis
- Management of neonatal sepsis
- regarding risks and consequences of neonatal sepsis, and
- Current diagnostic strategies and their perceived strengths and difficulties
- Perceptions of neonatal sepsis and how this might affect diagnosis and treatment
- Recommendations to enhance the diagnosis and treatment of neonatal sepsis

The focus groups will be conducted by members of MUJHU's social sciences team and [name]. A tool has been developed by the social sciences team and [name] for these discussions (see attached). The discussions will be recorded, and recordings destroyed once the discussions have been transcribed. The social sciences team will then complete thematic analysis of the discussions.

We anticipate Phase 1 will take place between January and July 2024.

Phase 2 will use the data collected in phase 1 to construct a risk stratification model, in collaboration with the Advanced Research Computing Centre at University College London.

We anticipate Phase 2 will take place between March and September 2024.

Using machine learning to model early-onset neonatal sepsis risk in Uganda (NeoRisk)

Phase 3 will involve external validation of the risk stratification tool. This phase will take place at Sally Mugabe Central Hospital in Harare, Zimbabwe. Participants will be recruited from antenatal clinics and labour wards by study staff.

The same data will be collected from participants in Phase 3 as in Phase 1. Ideally, data collection will take place via the Neotree platform(41) – this will be decided once the factors included in the model have been determined, and whether they are already in routine collection via Neotree. If the Neotree platform will not capture sufficient data to match the inputs of the model, an online CRF will be created as in Phase 1 via REDCap. This decision will be made in collaboration with the local study team prior to the start of recruitment.

The primary outcome for Phase 3 will be senior clinician diagnosis of sepsis recorded within 48 hours of delivery, and blood cultures (when available) will only be taken in neonates judged to be at risk of, or with clinical signs of sepsis as per standard clinical guidelines. Using senior clinician diagnosis of sepsis as the outcome is because supply of blood culture bottles and laboratory analysis of cultures is unreliable and is unlikely to be available to all study participants as in the Phase 1 setting. The risk stratification model will be applied to these data to determine its accuracy in a second population and explore its generalisability.

We anticipate Phase 3 will take place between September 2024 and March 2025.

The TRIPOD (Transparent reporting of a multivariable prediction model for individual prognosis or diagnosis) statement have been followed in the design of this study and will be followed in its reporting(42). Adjustments will be made as necessary with the release of upcoming artificial intelligence-specific guidelines.

Data analysis

Phase 2 will constitute the main data analysis for data from Uganda.

There will be two main streams to data analysis, which will be completed using R and in collaboration with the Advanced Research Computing Centre at UCL.

1. Machine learning analysis:
 - a. Data from Phase 1 will form a ‘training data set’, with 20% reserved for testing and validation, and be fed into a pre-programmed machine
 - b. Previous methods used for sepsis prediction that will be investigated include gradient tree boosting and neural networks
 - c. Bootstrapping will be considered
 - d. Determination of the exact machine learning model will depend on the data obtained, but the following will be considered:
 - i. Weighted inputs: Allows scaling of measurements
 - ii. Conformal prediction: Allows the machine to determine how uncertain its prediction is, based on distribution of data it has, and missing data
 - iii. Recurrent neural networks: Allows the machine to recognise time-dependent patterns
 - iv. Gradient descent: A method of ‘training’ a machine to minimise the error between prediction and reality by gradually adjusting its weights
2. Traditional logistic regression will be used to identify risk factors associated with clinical and microbiological diagnoses of neonatal sepsis. Although the principal model will be created using machine learning techniques, logistic regression will be

Using machine learning to model early-onset neonatal sepsis risk in Uganda (NeoRisk)

used as a second check of results and to provide additional context with which to interpret the machine learning model

For **Phase 3**, data will be inputted to the machine learning model from Phase 2, and the sensitivity, specificity, positive predictive and negative predictive values calculated, as well as the AUC value.

